##### **5.4.2.2. Deviations, Missing Concentrations and Anomalous Values**

In summary tables and plots of median profiles, concentrations will be set to missing if at least one of the following cases is true:

1. A concentration has been collected as ND (Not Done) or NS (no sample).
2. A deviation in sampling time is of sufficient concern or a concentration has been flagged anomalous by the pharmacokineticist.

Summary statistics will not be presented at a particular time point if more than 50% of the data are missing.

##### **5.4.2.3. Pharmacokinetic Parameters**

Noncompartmental parameters will not be calculated for the study report.

#### **5.4.3. Laboratory Assays Below the Limit of Detection**

Assays for some laboratory parameters have lower limits of detection (LLD). If the assay values are below the LLD, then it is equally likely to be anywhere between 0 and the LLD. In this case, the best single prediction of the value ignoring all other data from the subject is in the middle of 0 and the LLD value. As a general guidance for all data presentation except listings, the half of LLD value will be imputed for a laboratory assay value reported as below the LLD. For example,

1. For TFPI, value of “<3.0 ng/mL” will be imputed as 1.5 ng/mL.
2. For Cardiac Troponin I, value “<0.02 ug/L” will be imputed as 0.01 ug/L.
3. For D-dimer, value of “<190 ng/mL” will be imputed as 95 ng/mL.

In data listings assays with values below LLD will be reported as ‘<LLD’, where LLD will be replaced with the LLD value for the corresponding laboratory parameter.

#### **5.4.4. Handling of Incomplete Dates**

##### **5.4.4.1. Safety Endpoints**

For the analysis of safety endpoints, the sponsor data standard rules for imputation will be applied (eg, partial onset and resolved dates for AEs and concomitant medications will be imputed according to Pfizer standard algorithms). Dates that are derived for missing data by the Pfizer standard algorithms are bounded by square brackets accompanied by the footnote, “Days in brackets are imputed days derived from missing or incomplete dates.” in relevant data listings.

##### **5.4.4.2. Imputation Rules for Date of Last Contact**

The date of last contact will be derived for subjects not known to have died at the analysis cut-off using the latest complete date among the following:

- All subject assessment dates (blood draws including clinical laboratory, vital signs, immunogenicity sample, mRS, NIHSS, and health resource utilization).
- AE start and resolved dates

Only dates associated with actual examinations of the subject will be used in the derivation. Dates associated with a technical operation unrelated to subject status such as the date a blood sample was processed will not be used. Assessment dates after an analysis database cut-off date will not be applied to derive the last contact date.

#### **5.4.5. Extended Time Post Dose Visit Window**

The Schedule of Activities table in the study protocol defined the visit window and the study activities should take place within these visit windows. However, some activities such as laboratory testing, might occur out of the protocol specified visit window in reality. For the purpose of statistical analysis, Table 4 defines extended visit windows. If the deviation is determined not to compromise scientific integrity of the assessment upon review, and the result is obtained within the New Study Specified Visit Window for Statistical Analysis, then the result will be included in the analysis to minimize missing data issue.

**Table 4. Extended Visit Window for Analysis**

Visit Window Specified in Schedule of Activities Table in the Study Protocol		New Study Specified Visit Window for Statistical Analysis		
Study Day	Time Post Dose Visit Window	Extended Visit Window	Window Start	Window End
Day 1 Screening	Up to 6.0 hours pre-dose	[-24, 0] hr	-24 hr	0 hr

**Table 4. Extended Visit Window for Analysis**

Day 1	Hr 0	[-4,0] hr	-4 hr	0 hr
Day 1	Hr 0 Min 5 ( $\pm 2$ min)	$\pm 4$ min	1 min	9 min
Day 1	Hr 0 Min 45 ( $\pm 15$ min)	$\pm 30$ min	15 min	75 min
Day 1	Hr 3 and Hr 9 ( $\pm 30$ min)	$\pm 1$ hr	2 hr, 8 hr	4 hr, 10 hr
Day 2	24 Hr ( $\pm 6$ hr)	$\pm 8$ hr	16 hr	32 hr
Day 3	48 Hr ( $\pm 6$ hr)	$\pm 10$ hr	38 hr	58 hr
Day 4	72 Hr ( $\pm 6$ hr)	$\pm 12$ hr	60 hr	84 hr
Day 8/discharge	$\pm 24$ hr	$\pm 48$ hr	120 hr *	216 hr *
Day 43	$\pm 7$ Days	$\pm 12$ Days	720 hr (Day 31)	1296 hr (Day 55)
Day 91	$\pm 7$ Days	$\pm 12$ Days	1872 hr (Day 79)	2448 hr (Day 103)

\* For discharge day other than Day 8, use  $\pm 48$  hr from the discharge day to construct the extended visit window

If there are multiple measurements within a visit window, the measurement taken at the time that is closest to the scheduled visit time point will be used for summary statistics at that time point unless otherwise stated.

## 6. ANALYSES AND SUMMARIES

Refer to Section 3 for definitions of endpoints, Section 4 for definitions of analysis sets, and Section 5.3 for general methodology.

### 6.1. Primary Endpoints

#### 6.1.1. Treatment emergent TIEs through Day 8

The primary analyses will be based on the TIE-evaluable set. Treatment emergent TIEs will be listed and summarized overall and by dose group. The summary Tables include:

- Treatment emergent TIEs (all causalities) by system organ class and preferred term
- Treatment emergent TIEs (treatment related) by system organ class and preferred term
- Incidence and severity of treatment emergent TIEs (all causalities, treatment related)

As discussed in Section 5.2, the TIE data from the current cohort (and previous cohort[s]) will be utilized for the mCRM dose-toxicity modeling along with clinical and eDMC oversight to determine the MTD. The following Figures will be generated:

- Vertical bar chart of the number of treatment emergent TIEs by dose group used in the mCRM dose-toxicity modeling
- Estimated Dose-TIE toxicity response curve with 95% confidence interval around the fitted curve, superimposed on the number of subjects allocated to each dose group in a vertical bar chart format, and the observed proportion of treatment emergent TIE at each dose level
- Allocation of subjects at each dose and corresponding TIE toxicity response (red dot denotes treatment emergent TIE) showing how dose-escalation scheme progresses over time via the order of study enrollment and observed number of treatment emergent TIEs

For the interim analysis of the treatment emergent TIEs, refer to Section 7 for details.

#### **6.1.1.1. Sensitivity/Robustness Analyses**

One primary objective of this study is to determine the MTD of the study drug. The mCRM dose-toxicity modeling is based on an “intent-to-treat” approach that the subject’s assigned dose group is used in the modeling, estimation of MTD, and dose-recommendation for the next cohort based on available data during the safety review period after each respective cohort completes dosing. Sensitivity analysis will be conducted to assess the robustness of the MTD determination based on weight-based dosing. A confidence interval around the MTD may be calculated where appropriate. The relationship of the actual dose administered in  $\mu\text{g}$  with treatment emergent TIE occurrence will also be evaluated.

#### **6.1.2. Other Primary Safety Endpoints**

Other primary safety endpoints will be summarized descriptively by dose group. The endpoints include treatment emergent AEs through Day 8 and SAEs through Day 43 as characterized by type, frequency, severity, timing, seriousness and relationship to study treatment; treatment emergent laboratory abnormalities through Day 4 (Day 8/discharge for D-dimer); physician examination changes, vital signs changes, and ECG results through Day 8 (or discharge). Listings of data will be generated by dose group. Refer to Section 6.6 for details.

### **6.2. Secondary Endpoint(s)**

#### **6.2.1. Pharmacodynamic Endpoint**

The pharmacodynamic endpoint includes aPTT or PTT and PF1+2, within 2 days of dosing. Maximum change from baseline and area under the effect curve (AUEC) of change from baseline will be calculated for aPTT or PTT, and PF1+2.

The PD endpoints will be presented in tabular and/or graphical format and summarized descriptively, where appropriate. The summaries will be provided in actual values and change from baseline. Descriptive statistics including N, arithmetic mean, median, SD, minimum, and maximum will be used to summarize maximum change from baseline and AUEC of change from baseline.

#### 6.2.2. Immunogenicity Endpoint

Immunogenicity analysis will be conducted on the immunogenicity analysis set as defined in Section 4.3.3.

ADA, Nab and factor X activity assay results will be summarized by dose group and visit. The number and percentage of subjects with positive or negative ADA immune response and NAb immune response will be summarized by dose group in tabular format.

*An ADA immune response following study drug administration is defined as:*

- *A confirmed post-treatment positive assay result in combination with a negative baseline sample assay result; or*
- *A confirmed post-treatment positive assay result in combination with at least one dilution factor increase in titer relative to a positive baseline sample assay result.*

*Positive ADA responses to PF-05230907 will be further confirmed for cross reactivity against native FX and native FXa. Positive ADA responses will also be evaluated for neutralizing antibody immune response against PF-05230907. Neutralizing antibody immune responses will be assessed by results from a neutralizing assay and/or from the factor X activity assay.*

*A subject with neutralizing antibody immune response is defined as either:*

- *A positive result from at least one sample tested in the neutralizing assay; or*
- *Depletion of study subject factor X activity (>50% reduction relative to baseline) in the basal state, at assessments subsequent to study drug administration in combination with a demonstrated positive ADA immune response and in the absence of any other plausible explanation for decline in factor X activity.*

*In the presence of ADA to PF-05230907 that is cross reactive with native FX or native FXa, a positive neutralizing antibody response against PF-05230907 will be imputed to be cross reactive against native FX or native FXa respectively.*

### **6.3. Exploratory Endpoint(s)**

Exploratory efficacy measures include hemostatic endpoints (ICH absolute and **CCI** [REDACTED] from baseline volume) and neurological outcomes (mRS and NIHSS).

Descriptive statistics will be used to summarize selected exploratory endpoints by dose group, where appropriate. Change from baseline for selected continuous measure will be summarized descriptively. Listings of all exploratory endpoint information will be generated by dose group.

Analyses to be conducted on each exploratory endpoint and associated measures at other time points are described in each subsection below.

#### **6.3.1. Hemostatic Endpoint**

##### **6.3.1.1. ICH change from baseline**

*ICH absolute and **CCI** [REDACTED] from baseline volume at 24 hours* are exploratory endpoints. ICH volume obtained from central vendor will be used for the evaluation of these endpoints to reduce variability and enhance accuracy of the results reported.

Absolute change from baseline and **CCI** [REDACTED] from baseline in ICH volume will be summarized descriptively.

##### **6.3.1.2. CT parameters**

Another exploratory endpoint includes CT parameters that may inform future investigations of PF-05230907 and/or the condition of ICH.

Actual values in edema volume contiguous with the area of hemorrhage, and volume of blood in ventricle will be summarized descriptively and presented in tabular format, where appropriate. New onset ischemic components not contiguous with the area of hemorrhage, absent at baseline but present at 72 hours will also be summarized if applicable. The number and percentage of subjects in each of the following categories may be summarized in tabular format:

- location of origin of bleed
- location of ischemic component
- presence of “swirl sign” on baseline CT
- presence of spot sign on baseline CT angiogram (if applicable)
- pre-existing ischemia not contiguous with hemorrhage
- location of pre-existing ischemia not contiguous with hemorrhage

- new onset ischemia not contiguous with hemorrhage
- location of new onset ischemia not contiguous with hemorrhage

The diagnostic brain CT scan completed within 6.0 hours from subject's spontaneous ICH symptom onset will provide a baseline assessment of ICH volume assessed by the ABC/2 method,  $ICH_{ABC}$ , for purposes of determining study eligibility. Correlation between the baseline ICH volume obtained by ABC/2 method and the central vendor will be assessed. In addition, the time since ICH onset to study drug start, the time elapsed between baseline CT scan and the study drug start time will be summarized.

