3. STUDY DESIGN

This is a Phase 1b, multi-center, open-label study to determine the maximum tolerated dose (MTD) and assess the safety and tolerability, and PD of PF-05230907 administered once as an IV bolus in subjects with ICH. A modified continual reassessment method (mCRM) design based on the endpoints of treatment emergent thromboembolic and/or ischemic events (TIEs) will be adopted. The mCRM design utilizes Bayesian methodology to continuously learn the dose-toxicity relationship, which is characterized by a parametric model. The starting dose will be 5 µg/kg based on the highest dose safely administered in the first in human (FIH) clinical study (B2341001).

As safeguards for subject safety, (a) dose escalation will be conducted in a limited number of subjects per cohort (N=3), (b) sequential dosing of study subjects will be implemented in each cohort evaluating a dose level that exceeds previously administered dose levels and rules will apply governing additional cohorts at the respective dose level that are subject to sequential dosing (section 3.1), (c) dosing will be paused following completion of each cohort until safety is assessed for the respective cohort, (d) safety laboratory biomarker criteria are implemented which trigger smaller maximum increments for dose escalation ([Section 3.2](#)) (e) enrollment of the next cohort will not proceed until a safety review has completed for the preceding cohort and the chair of the eDMC has provided authorization ([Section 3.3](#)) and (f) criteria are implemented which trigger an automatic eDMC review of safety at a respective dose level ([Section 3.3](#)).

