6.2.8. Day 4 (72 Hours ±6 Hours)

Subjects in the study must stay in the hospital/stroke unit/ICU at a minimum through Day 4.

The following procedures will be completed:

- Complete targeted physical examination: physical examination should consist of assessments of general appearance, skin, heart (auscultation), lungs (auscultation), abdomen (palpitation and auscultation), and extremities with attention to swelling, general or localized tenderness, entire leg or calf swelling, edema, and collateral superficial veins.
- Collect vital signs: including temperature, blood pressure, pulse rate, and respiratory rate (supine).
- Collect ECG: single standard supine 12-lead ECG will be collected.
- Obtain CT or MR scan: CT or MR scan will be completed and reviewed locally for evidence of a treatment emergent ischemic event and sent to central vendor for final analysis. CT scan is the preferred imaging modality however for the Day 4 assessment a site may substitute an MR scan based on local standard of care (SoC), local regulatory, or clinical considerations at the investigator's discretion.
- Collect the following blood samples:
 - Safety:
 - D-dimer sample collection to be processed at **local** laboratory.
 - Cardiac troponin I sample collection to be processed at local laboratory (or cardiac troponin T, where applicable) or shipped to a central laboratory.

- Blood chemistry, PT/INR, fibrinogen, ATIII, Protein S level, Protein C activity, and hematology (WBC count, differential, hematocrit, hemoglobin, platelet) sample collections for shipment to a central laboratory.
- For sites in Germany, PT/INR, fibrinogen, and hematology safety labs should also be analyzed locally.
- PD sample collection (aPTT/PTT and exploratory biomarkers) for shipment to a central laboratory.
- Neuro-inflammation biomarker sample collection for shipment to a central laboratory.
- Obtain lower extremity Doppler Ultrasonography; no nicotine intake should occur for approximately 1 hour prior to testing.
- Complete Thrombosis Clinical Probability Scores.
 - Review Wells' algorithm ([Appendix 2](#)).¹⁵ If indicated, obtain pulmonary imaging study.
- Conduct the mRS.
- Conduct the NIHSS.
- Monitoring of serious adverse events.
- Monitoring of adverse events.
- Monitoring of concomitant medications and treatments.

If Day 4 is the date of discharge then the following additional procedures should be completed:

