7.1.7. CT or MR Scan at Day 4 (72 Hours Post-dose)

A CT or MR scan will be completed as indicated in the [Schedule of Activities](#) and reviewed locally by a qualified physician for evidence of a treatment emergent ischemic event at Day 4 (72 hours post-dose). CT scan is the preferred imaging modality however for the Day 4 assessment a site may substitute an MR scan based on local standard of care (SoC), local regulatory, or clinical considerations at the investigator's discretion. Clinically significant results that represent changes from the Day 2 (24 hour post-dose) imaging should be considered for recording as AEs or SAEs per protocol [Section 8](#). The scan will be sent to central vendor for final analysis.

7.1.8. TIEs Through Day 8

TIEs ([Appendix 1](#)) are to be reported by the study site following protocol [Section 8.6.1](#) and [Section 8.14](#). The dose toxicity relationship for each cohort is based upon the TIE data and is reviewed as part of the mCRM design, therefore it is essential these events be reported as AEs or SAEs in a timely manner by the study site.

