Cardiac troponin I increased	3	1: Levels above the upper limit of normal and below the level of myocardial infarction as defined by the manufacturer 2: Not defined 3: Levels consistent with myocardial infarction as defined by the manufacturer 4: Not defined 5: Not defined
Ischemia cerebrovascular	1 or higher and associated with lesion(s) on CT/MRI not contiguous with the ICH lesion and in a discrete separate area of the brain	1: Asymptomatic; clinical or diagnostic observations only; intervention not indicated 2: Moderate symptoms 3: Not defined 4: Not defined 5: Not defined

Adverse Event	Grade Defining a TIE	Grade and Description
Portal vein thrombosis	2 or higher	1: Not defined 2: Intervention not indicated 3: Medical intervention indicated 4: Life-threatening consequences; urgent intervention indicated 5: Death
Ischemic stroke based upon CTCAE V4.03 toxicity criteria for stroke	1 or higher and associated with lesion(s) on CT/MRI not contiguous with the ICH lesion and in a discrete separate area of the brain	1: Asymptomatic or mild neurologic deficit; radiographic findings only 2: Moderate neurologic deficit 3: Severe neurologic deficit 4: Life-threatening consequences; urgent intervention indicated 5: Death

Adverse Event	Grade Defining a TIE	Grade and Description
Transient Ischemic attacks	2	1: Mild neurological deficit with or without imaging confirmation 2: Moderate neurologic deficit with or without imaging confirmation 3: Not defined 4: Not defined 5: Not defined
Purpura	2 or higher	1: Combined area of lesions covering <10% BSA 2: Combined areas of lesions covering 10-30% BSA; bleeding with trauma 3: Combined areas of lesions covering >30% BSA; spontaneous bleeding 4: Not defined 5: Not defined

Adverse Event	Grade Defining a TIE	Grade and Description
Superior vena cava syndrome	1 or higher	1. Asymptomatic; incidental finding of SVC thrombosis 2. Symptomatic; medical intervention indicated (eg, anticoagulation, radiation, or chemotherapy) 3: Severe symptoms; multi-modality intervention indicated (eg, anticoagulation, chemotherapy, radiation, stenting) 4: Life-threatening consequences; urgent multi-modality intervention indicated (eg, lysis, thrombectomy, surgery) 5: Death

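### Protocol 7.1.7 sets a narrower recording test for Day 4 imaging than Appendix 1 sets for a TIE, so a silent new ischemic lesion can appear in the SAP imaging tables yet be missing from the TIE count and the dose-TIE fit

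*SAP*

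**What the plan says.** **Definition.** For cerebrovascular ischemia and ischemic stroke, Protocol Appendix 1 (repeated in SAP Appendix 1) sets the TIE grade at "1 or higher and associated with lesion(s) on CT/MRI not contiguous with the ICH lesion and in a discrete separate area of the brain". Grade 1 covers an asymptomatic, imaging-only finding. SAP 3.1.1 adds that onset or worsening must fall between dosing and Day 8. It sets no condition of clinical significance.

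**Reporting.** Protocol 7.1.8 says TIEs "are to be reported by the study site following protocol" sections 8.6.1 and 8.14, and calls timely reporting essential because the mCRM depends on it.

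**Day 4 scan.** Protocol 6.2.8: "CT or MR scan will be completed and reviewed locally for evidence of a treatment emergent ischemic event and sent to central vendor". Protocol 7.1.7 then gives the recording test: "Clinically significant results that represent changes from the Day 2 (24 hour post-dose) imaging should be considered for recording as AEs or SAEs". It also says: "The scan will be sent to central vendor for final analysis".

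**Day 2 scan.** Protocol 6.2.6 says only that this CT goes to a central vendor. It gives no instruction for a local read for ischemia.

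**SAP imaging tables.** Section 6.3.1.2 (exploratory) says: "New onset ischemic components not contiguous with the area of hemorrhage, absent at baseline but present at 72 hours will also be summarized", where applicable. Section 6.6.6.2 summarises the same finding as safety data, also against baseline. Neither names the read used for ischemia, and neither refers to the TIE count.

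**Precedence.** Protocol 7.1.6 and SAP 6.6.2 put central troponin I above local troponin T. No corresponding rule exists for imaging.

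**The concern.** Appendix 1 and 7.1.8 say that a silent, separate, post-dose lesion is a TIE and must be reported. Section 7.1.7, the one passage that tells a site what to do with the Day 4 result, applies two filters that Appendix 1 lacks: clinical significance and change from Day 2. It also makes recording a matter for consideration. A site that follows 7.1.7 as written can leave out an event that Appendix 1 counts.

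TIE frequency is the first primary endpoint and the only outcome that enters the mCRM. Protocol 3.2 and SAP 5.2.3 say that other safety events do not affect the model's recommendation. If a subject has no other TIE, an uncounted lesion lowers the TIE count and can only raise the estimated MTD or leave it unchanged. The study is open-label with no control arm, so nothing elsewhere in the data would reveal the loss. One report could show more subjects with new separate ischemia in an imaging table than with cerebral TIEs in the primary table, with no rule for explaining the difference.

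**Working it through.** **1. Two lesions traced through the text.** Both are silent, absent at baseline, non-contiguous with the ICH, in a discrete separate area, and present at 72 h.

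| | A: first visible after the Day 2 scan | B: already visible on the Day 2 scan |
|---|---|---|
| Appendix 1, Grade 1 | TIE | TIE |
| 7.1.8 | report | report |
| 7.1.7, change from Day 2 | met | not met if unchanged |
| 7.1.7, clinically significant | may fail | may fail |
| SAP 6.3.1.2 and 6.6.6.2, against baseline | tabulated | tabulated |

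Protocol 8.5 does not settle either case. A silent finding that needs no further test, treatment or change in participation becomes an AE only under its last criterion, that the investigator or sponsor considers it one.

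**2. Reproducing the plan's model.** The inputs are in SAP 5.2: the Table 3 rates p, the prior β ~ Unif[0,3], a 15% target, and a cap of two increments above the highest dose studied. The adjusted dose is x = atanh(2p − 1). For 5 µg/kg, p = 0.08 and x = atanh(−0.84) = −1.22, as printed. All 15 values match Table 3 to two decimals.

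**3. One TIE counted or not, first cohort (3 subjects at 5 µg/kg).** With p^β as the modelled rate, the output is the highest grid dose with p^β̂ below 0.15, where β̂ is the posterior mean found by numerical integration.
- 0/3 counted: posterior ∝ (1 − 0.08^β)³ and β̂ = 1.82. At 19 µg/kg, 0.325^1.82 ≈ 0.13; at 24 µg/kg, 0.38^1.82 ≈ 0.17. Output 19, capped to 8.
- 1/3 counted: posterior ∝ 0.08^β(1 − 0.08^β)² and β̂ = 0.72. At 4 µg/kg, 0.06^0.72 ≈ 0.13; at 5 µg/kg, 0.08^0.72 ≈ 0.16. Output 4.

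**4. Later cohorts.** On an otherwise TIE-free path, the next capped output with the current cohort's single TIE counted, against not counted, is:
- cohort 2: 10 against 12
- cohort 3: 15 against 19
- cohort 4: 19 against 30
- cohort 5: 24 against 30
- cohorts 6 and 7: no change

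For a 21-subject path 5-8-12-15-19-19-24 with one TIE at 12, the model estimate is 24. One further TIE gives 19, or 15 if it occurred at 5. These figures show how the plan's algorithm responds; they are not dose proposals.

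**5. Range under assumed capture.** Suppose a fraction s of TIEs is counted at every dose, with no false positives. A counted rate of 15% then corresponds to a true rate of 15%/s. The documents give no value for s. The values below assume a share of TIEs that are silent and a fraction of those that are missed.
- 25% silent, half missed: s = 1 − 0.25 × 0.5 = 0.875, true rate 17.1%
- 50% silent, half missed: s = 0.75, true rate 20%
- 50% silent, all missed: s = 0.5, true rate 30%

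A simulation of 1,500 trials per case, with Table 3 as the true curve and the stopping rules coded from the text, gave a mean true TIE rate at the selected dose of 16.4% with full capture. In the three cases above it was 18.5%, 21.8% and 29.4%.

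**The case against.** The strongest reply is that 7.1.8 already governs. Appendix 1 events must be reported, SAP 3.1.1 has no clinical-significance condition, and 6.2.8 has the Day 4 scan read locally for treatment-emergent ischemia. A site that omits a Grade 1 separate lesion departs from 7.1.8. This stands to the extent that no rule excludes silent lesions. The defect is that 7.1.7 gives the site a conflicting and looser instruction for the same scan.

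A reader might infer that the site's read alone decides TIE status. The documents do not support that. Sponsor and investigator documentation of TIEs is mandatory at Day 8 (Protocol 6.2.9). The sponsor reviews safety data and discusses each subject with the investigator before the next cohort (3.2), and may deem a result an AE (8.5). The medical monitor sees 72-hour imaging during sequential dosing (3.1), and the medical monitor and eDMC chair see significant imaging findings between cohorts (SAP 7.4.2). These steps reduce the risk, but none is tied to the central final analysis.

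A reader might also infer that the central read goes only to the CT-parameter table. That rests on silence. SAP 6.3.1.2 names no reader for ischemia, 6.6.6.2 summarises the finding beside text on local review, and SAP 3.3.1 mentions the vendor only for the baseline and 24-hour scans.

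Finally, the dose figures show sensitivity to one event, not how often events are lost. The effect fades by cohorts 6 and 7, and the 21-subject path has too few subjects at any dose to declare an MTD under SAP 5.2.4. That is correct, and the figures are used here only as illustration.

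**Conclusion.** The conflict is in the text and should be resolved. Section 7.1.7 applies a test that Appendix 1 and 7.1.8 do not, the SAP tables use a different comparator, and no passage carries a lesion seen only on the central read, or one tabulated only against baseline, into the TIE count. The direction is towards undercounting and a higher estimated MTD. The size cannot be derived because no local/central disagreement rate is given. One event in the first cohort changes the capped output from 4 to 8 µg/kg. The 17.1% to 30% range rests on assumed capture, constant across doses, with perfect specificity.

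A reader might conclude that the primary TIE table should be recounted on central reads. The documents do not support that. Absence on baseline CT and presence on Day 4 MR is not proof of onset after dosing, and a rule based on non-contiguity alone would drop Appendix 1's discrete-separate-area condition. Protocol 9 and SAP 2 require an amendment for a major change to the primary endpoint or its analysis. The SAP amendment postdates termination after 21 subjects, so a recount would be post hoc. Termination does not remove the issue, because SAP 6.1.1 still calls for TIE tables and a fitted dose-TIE curve.

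**What to change.** 1. Reconcile Protocol 7.1.7 with Appendix 1 and 7.1.8, so that recording a post-dose lesion that meets an Appendix 1 row does not depend on clinical significance or on change from the Day 2 scan only.
2. In SAP 6.1.1.1, keep the reported TIEs as primary. Add a sensitivity TIE table and dose-TIE fit that also count subjects whose central read shows a new post-baseline lesion meeting the full Appendix 1 wording: not contiguous with the ICH and in a discrete separate area.
3. List local/central disagreements, and flag subjects whose baseline CT is compared with a Day 4 MR.
4. State in SAP 6.3.1.2 and 6.6.6.2 which read each ischemia table uses.

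The cost is a short protocol clarification, a few SAP sentences, one extra model run and one listing. The scans already go to the central vendor, so no new reader or procedure is needed. The drawback is that the sensitivity count may exceed the count used for escalation and may include central false positives, which is why it stands beside the primary result and does not replace it.
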